### **4. PLANNED ANALYSES**

### 4.1. DATA MONITORING COMMITTEE (DMC)

There is no DMC planned for this study.

### 4.2. INTERIM ANALYSIS

No interim analysis for efficacy or safety is planned for this study.

### **4.3. FINAL ANALYSIS**

The final analyses identified in this SAP will be performed by Biostatistics following Sponsor Authorisation of this SAP, Database Lock, and Sponsor Authorisation of Analysis Sets and unblinding of Treatment.

### 5. ANALYSIS SETS

Agreement and authorisation of subjects included/excluded from each analysis set will be conducted prior to the unblinding of the treatment allocations. A blinded data review plan will be created and further details related to analysis sets and major protocol deviations will be described in this plan.

### **5.1.** INTENT-TO-TREAT (ITT) POPULATION

The ITT population will include all randomised subjects irrespective of whether any study medication was ingested. In this population, treatment will be assigned based upon the treatment arm to which subjects were randomised regardless of which treatment they actually received.

### **5.2.** PER PROTOCOL POPULATION (PP)

The PP population will include all randomised subjects who do not have major protocol deviations that would affect the evaluation of the primary efficacy endpoint.

A major protocol deviation that is considered to affect the primary efficacy endpoint will lead to exclusion of subjects from the PP population. Major protocol deviations considered to affect the primary analysis include, but are not limited to, the following;

- 1. Violations of the inclusion/exclusion criteria
  - a. The following inclusion criteria should be fulfilled:

# % VHsquared

STATISTICAL ANALYSIS PLAN: PROTOCOL V56502

Page 13 of 40

- i. Inclusion criterion 2: CDAI score of ≥220 to ≤450 during Screening
- ii. Inclusion criterion 3: CRP  $\geq$ 5 mg/L (or, if CRP is normal, FCP  $\geq$ 250 µg/g) at screening.
- iii. Inclusion criterion 4: Active CD of ileum and/or colon as determined by the baseline ileocolonoscopy
- b. The following exclusion criteria should be absent in the data for the subjects:
  - i. Exclusion criterion 3: Any gastrointestinal (GI) manifestations of CD that might affect the evaluation of efficacy.
  - ii. Exclusion criterion 5: Prior primary efficacy failure of or secondary loss of response to anti-TNFα therapy, or any contraindication to anti-TNFα therapy
  - iii. Exclusion criterion 6: The use of medications prior to the study or during the study with the potential to affect the evaluation of efficacy.
- 2. Mishandling of the study drug which could have impacted the integrity of the study data such as nonallowable temperature deviations during storage or dispensing of study drug to the wrong subject
- 3. Non-compliance rate of <80% or >120% with study treatment.
- 4. Use of prohibited concomitant medications.
- 5. Study procedures done outside protocol-specified window period that are judged to affect study efficacy data.
- 6. Assessments for primary endpoint not done.

Protocol deviations will be reviewed prior to unblinding and individual subjects having protocol deviations will be evaluated for inclusion in the PP population. Any additional deviations not listed above will be documented at this time.

### 5.3. SAFETY POPULATION (SAF)

The SAF population will include all randomised subjects who receive at least one capsule of V565/placebo. In this population, treatment will be assigned based upon the treatment subjects actually received, regardless of the treatment to which they were randomised.

### **5.4.** PHARMACOKINETIC POPULATION (PK)

The PK population will include all subjects in the SAF population who receive at least one capsule of V565 and who have at least one pre dose sample of serum or urine and who do not have events or protocol deviations with the potential to affect serum PK or urine PK concentrations.

Changes to the procedures or events, which may impact the quality of the PK data will be described within the clinical study report body text. These changes or events will include any circumstances that will alter the evaluation of the PK. Examples include, but may not be limited to,

- 1. sample processing errors that lead to inaccurate bioanalytical results,
- 2. inaccurate dosing on the day of PK sampling due to administration incidents or lack of compliance with

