### Criteria for evaluation:

Primary Efficacy Endpoint:

 Proportion of responders at Day 42, defined as subjects achieving both CDAI ≥70-point reduction from Baseline OR CDAI score <150, AND a reduction of ≥40% from the baseline value of CRP or FCP

Secondary Efficacy Endpoints:

- Proportion of subjects achieving a ≥100-point reduction in CDAI score and a concomitant reduction of 50% in CRP or FCP at Day 42
- Proportion of subjects achieving a  $\geq$ 70-point reduction in CDAI score at Day 42
- Proportion of subjects achieving a  $\geq$ 100-point reduction in CDAI score at Day 42
- Proportion of subjects achieving a CDAI score of <150 CDAI at Day 42
- Changes from Baseline in scores for PRO-2 at Day 14 and Day 42

Safety Endpoints:

• Evaluations of AEs, clinical laboratory results, physical examination findings, ECGs and vital signs throughout the study

Pharmacokinetic Endpoint:

• Serum and urine concentration of V565 prior to first administration of study drug and at Day 14, Day 42, and Day 56. In addition, On Day 1, a post-dose urine sample will be obtained at the site 4 to 8 hours after the first dose of study drug.

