### 8.2.3 Exploratory Analyses

The exploratory endpoint evaluating the proportion of subjects achieving CRP (or FCP) levels within normal limits at Day 14 and Day 42 will be summarised using frequency and percentage.

The endpoints evaluating changes in CDAI score over time and changes in CRP (or FCP) results over time will be summarised using descriptive statistics.

The anti-V565 antibody responses will be summarised and listed for the safety (SAF) population.

In the exploratory endoscopy substudy, changes in the central reader's overall assessment and changes in SES-CD from Baseline to Day 42 will be summarised using descriptive statistics. Summary statistics presentation will be separated for subjects with ileum and colon involvement and for subjects with only ileal mucosal lesions.

Any additional analyses or data presentation details will be described in the SAP.

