### 8.2.7 Analysis Populations

Intent-to-Treat (ITT) population: The ITT population will include all randomised subjects. In this population, treatment will be assigned based upon the treatment arm to which subjects were randomised regardless of which treatment they actually received.

Per Protocol population (PP): The PP population will include all subjects who do not have major protocol violations that would affect the evaluation of the primary efficacy endpoint.

Safety population (SAF): The SAF population will include all randomised subjects who receive at least one dose of study drug. In this population, treatment will be assigned based upon the treatment subjects actually received, regardless of the treatment to which they were randomised.

Pharmacokinetic population (PK): The PK population will include all subjects in the SAF population who receive at least one dose of study drug and who have at least one post dose sample of serum and urine who do not have events or protocol deviations with the potential to affect PK concentrations.

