# 😵 VHsquared

STATISTICAL ANALYSIS PLAN: PROTOCOL V56502 Page 14 of 40

the protocol,

- 3. dosing date/time not available
- 4. blood/urine sampling date and time not available.

Affected data will be evaluated by the pharmacokineticist to determine whether or not they can be included in the PK analysis. Other changes to the procedures or events which do not impact the quality of the PK data will not be considered significant protocol deviations. A common example of a non-significant protocol deviation is a missed blood sample or deviations from blood collection times.

Protocol deviations will be reviewed prior to unblinding and individual subjects having protocol deviations with the potential to affect PK concentrations will be evaluated during the blinded data review meeting for inclusion in the PK population.

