### 5.6. **IMMUNOGENICITY POPULATION**

The immunogenicity population will include all subjects in the SAF population who receive at least one capsule of V565/placebo and who have at least one pre dose sample of serum and who do not have events or protocol deviations with the potential to affect immunogenicity.

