### **16.** PHARMACOKINETIC ANALYSIS

Individual PK serum blood sample collection dates/times, and the associated V565 concentrations will be listed by visit for each subject.

The PK urine sample collection dates/times and V565 excreted will be listed by visit for each subject. The amount excreted will be determined as V565 concentration × urine volume of the urine sample at the visit.

Serum and urine V565 concentrations will be summarized using descriptive statistics by visit on the PK population.

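### SAP 5.4 selects the PK population on a pre-dose serum or urine sample where the protocol requires post-dose serum and urine, and SAP 3.3 declares neither change

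*SAP*

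**What the plan says.** Protocol 8.2.7 builds the PK population from treated subjects "who have at least one post dose sample of serum and urine", without events or deviations likely to affect concentrations. SAP 5.4 keeps the treatment and deviation conditions but admits subjects "who have at least one pre dose sample of serum or urine".

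The PK endpoint in the protocol synopsis is "Serum and urine concentration of V565 prior to first administration of study drug and at Day 14, Day 42, and Day 56", with one further urine sample after the first dose on Day 1. There is thus one time point before dosing and several after it.

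The set has a use. SAP 16 states: "Serum and urine V565 concentrations will be summarized using descriptive statistics by visit on the PK population".

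SAP 3.3 sets out changes from the protocol's analysis. Its text concerns the CRP and FCP covariates and the biomarker part of the response definition. It says nothing about the PK population.

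SAP 5.6 adds an immunogenicity population, which the protocol does not have, for V565 or placebo subjects "who have at least one pre dose sample of serum". For antibody results the protocol (8.2.3) uses a different set: "The anti-V565 antibody responses will be summarised and listed for the safety (SAF) population". SAP 17.6 also lists them on the safety population.

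**The concern.** A PK population should contain the subjects in whom exposure can be assessed. A sample taken before the first capsule cannot show exposure to V565, so having one is not a test of PK evaluability. The SAP rule can therefore go wrong in two directions: it can leave out a subject with usable post-dose concentrations, and it can count a subject who has none.

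Low systemic exposure is central to the product's rationale (protocol 2.2). In Phase 1 the drug was not found in any serum sample and was found in the urine of one subject with Crohn's disease (protocol 2.1). When detections are that rare, the set of subjects behind the concentration summaries should be the one the protocol defined, or the change should be stated and explained.

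**Working it through.** The plan gives no figure to reproduce, so the check is a comparison of the two rules.

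| Element | Protocol 8.2.7 | SAP 5.4 |
|---|---|---|
| Timing of the qualifying sample | post-dose | pre-dose |
| Matrices | serum and urine | serum or urine |
| Declared in SAP 3.3 | – | no |

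**Does pre-dose mean before the first dose?** The endpoint has a single time point before first administration. Protocol 6.5.1 records the most recent dose before PK sampling on Days 14 and 42, so those samples follow dosing. SAP 17.6 attaches the term to Day 1. Nothing in the documents gives it a wider meaning, such as a trough sample at a later visit.

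**Which subjects change status?** Four samples can each be present or absent: pre-dose serum, pre-dose urine, post-dose serum, post-dose urine. That gives 2 × 2 × 2 × 2 = 16 patterns.

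- Protocol rule (both post-dose samples present): 1 post-dose combination × 4 pre-dose combinations = 4 patterns.
- SAP rule (at least one pre-dose sample present): 3 pre-dose combinations × 4 post-dose combinations = 12 patterns.
- Both rules: 3 × 1 = 3.
- SAP only: 12 − 3 = 9. Of these, 3 × 1 = 3 have no post-dose sample at all, and the other 6 have exactly one post-dose matrix.
- Protocol only: 4 − 3 = 1. This subject has post-dose serum and urine but neither pre-dose sample.
- Neither rule: 16 − 3 − 9 − 1 = 3.

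These are counts of logical patterns, not of expected subjects.

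**Which change does the damage?** Suppose only the connector had changed, giving post-dose serum or post-dose urine. That rule admits 3 × 4 = 12 patterns. Every one has some post-dose data, and all 4 protocol patterns are kept. The wrongful exclusion and the admission of subjects with no exposure information both come from the timing. The connector change is a separate loosening. It may be sensible, since serum and urine concentrations are distinct measurements, but it is still undeclared.

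**The case against.** The strongest reply is that this is probably a one-word slip with little consequence. Much of that stands.

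- Exclusion requires *both* pre-dose samples to be missing, and protocol 4.2.2 has the Day 1 procedures completed before treatment starts. It should be uncommon.
- An excluded subject's concentrations still appear in the by-subject listings; only the summaries lose them.
- The PK analysis is descriptive, and the primary efficacy analysis is on the ITT population.

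None of this answers the mismatch itself or its absence from SAP 3.3.

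Four stronger readings are tempting, and the documents do not support them.

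- *Subjects with only a pre-dose sample dilute a detection rate.* SAP 6 defines the summary count as non-missing cases, so such subjects add nothing at Day 14, 42 or 56. Neither document plans a detection rate or an upper confidence bound on the PK population.
- *The planned dropout (84 − 76 = 8 V565 subjects) measures the problem.* That equates leaving early with having no post-dose sample. Samples are due on Day 14, at the Early Termination Visit and, if possible, on Day 56, and post-dose urine is due on Day 1.
- *SAP 5.4 contradicts itself by saying "A common example of a non-significant protocol deviation is a missed blood sample".* That sentence classifies protocol deviations. A minimum-sample rule for entering the set is a separate matter.
- *SAP 5.6 makes the same error and inflates an antibody denominator.* The protocol has no immunogenicity population to contradict. The objective is change in titre (protocol 3.1.4), so the pre-dose sample is the necessary baseline. Antibody results are reported on the safety population, and SAP 17.6 plans listings of titres, not an incidence rate. In the text available, the SAP 5.6 set appears only in the population counts and exclusion listings of SAP 9. The criterion is incomplete, because it does not ask for a post-dose sample, but the sample it asks for is not the wrong one.

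**Conclusion.** The point holds for the PK population. SAP 5.4 reverses the timing of the qualifying sample and loosens the matrix requirement relative to protocol 8.2.7, without declaring either. Applied literally, it drops a V565 subject with complete post-dose data and no pre-dose sample from the by-visit summaries, and it counts as PK-evaluable a subject with no exposure information.

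The consequence is minor. It is confined to the descriptive PK summaries and to the population counts and reasons for exclusion. No size can be put on it, because the documents give no rate of missing pre-dose or post-dose samples. The conclusion assumes that pre-dose means before the first dose, as the SAP's own usage indicates, and that the rule is programmed as written. For immunogenicity, only the absence of a post-dose requirement survives, and it matters only if the SAP 5.6 set is used for an output beyond those described.

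**What to change.** Before database lock:

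1. In SAP 5.4, replace the pre-dose condition with at least one post-dose sample.
2. Reconcile *and* with *or* against protocol 8.2.7. One workable form applies the rule by matrix: post-dose serum for the serum summary, post-dose urine for the urine summary.
3. Record in SAP 3.3, with a reason, whatever still differs from the protocol.
4. In SAP 5.6, state whether the set supports any output. If it does, keep the pre-dose serum sample as baseline and add a post-dose serum sample for V565 subjects only. SAP 17.6 lists placebo titres only at Day 1 before dosing, so a blanket post-dose rule could remove the placebo arm if only those samples are assayed.

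The cost is a few lines of SAP text and a matching edit to the derivation of the population flags. No new data are needed.

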# 😵 VHsquared

STATISTICAL ANALYSIS PLAN: PROTOCOL V56502 Page 14 of 40

the protocol,

- 3. dosing date/time not available
- 4. blood/urine sampling date and time not available.

Affected data will be evaluated by the pharmacokineticist to determine whether or not they can be included in the PK analysis. Other changes to the procedures or events which do not impact the quality of the PK data will not be considered significant protocol deviations. A common example of a non-significant protocol deviation is a missed blood sample or deviations from blood collection times.

Protocol deviations will be reviewed prior to unblinding and individual subjects having protocol deviations with the potential to affect PK concentrations will be evaluated during the blinded data review meeting for inclusion in the PK population.

### 5.6. **IMMUNOGENICITY POPULATION**

The immunogenicity population will include all subjects in the SAF population who receive at least one capsule of V565/placebo and who have at least one pre dose sample of serum and who do not have events or protocol deviations with the potential to affect immunogenicity.

### 6. GENERAL CONSIDERATIONS

The following descriptive statistics will be presented in summary tables:

- Continuous variables: number (non-missing cases), mean, median, standard deviation (SD), minimum, and maximum
- Categorical variables: will be summarised by treatment group using frequency tables (frequencies and percentages). Percentages are routinely based on the total category count excluding the missing category if not otherwise mentioned. Missing category with zero count will not be presented

In general, the number of decimal places displayed for each statistic will be determined as follows with a maximum of three decimal places:

- Mean and median: one more than the number of decimal places allotted in the raw data received from data management
- SD: two more than the number of decimal places allotted in the raw data

- Minimum and maximum: equal to the number of decimal places allotted in the raw data
- Confidence Intervals (CIs) will be presented using the number of decimal places plus one as the parameters (e.g. mean) as appropriate
- P-values greater than or equal to 0.0001, in general, will be presented to four decimal places. P-values less than 0.0001 will be presented as "<0.0001" and p-value greater than ">0.9999" will be presented as 1.0000
- Percentages will be reported to one decimal place

In the case of normality assumption violations, appropriate non-parametric methods will be used for analysis as mentioned in section 15.2.3

Coding of adverse events and medications data (i.e. by Medical Dictionary for Regulatory Activities [MedDRA 19.1] or World Health Organization [WHO]-drug dictionary 01Sep2016E) will be included in the datasets.

### 6.1. **REFERENCE START DATE AND STUDY DAY**

Study Day will be calculated from the reference start date and will be used to show start/ stop day of assessments and events.

Reference start date is defined as the day of the first dose of study drug, (Day 1 is the day of the first dose of study drug) and will appear in every listing except medical history where an assessment date or event date appears.

If the date of the event is on or after the reference date then:

Study Day = (date of event - reference date) + 1

• If the date of the event is prior to the reference date then:

Study Day = (date of event – reference date)

In the situation where the event date is partial or missing, the date will appear partial or missing in the listings, and Study Day, and any corresponding durations will be presented based on the imputations specified in appendix 2; Partial Date Conventions.

### 6.2. BASELINE

Unless otherwise specified, baseline is defined as the last non-missing measurement taken prior to first administration of study drug (including unscheduled assessments). In the case where the last non-missing measurement and the reference start date coincide, that measurement will be considered pre-baseline, but Adverse Events (AEs) and concomitant medications commencing on the reference start date will be considered post-baseline.

For the endpoints of CRP and FCP, the baseline score is the last non-missing measurement taken prior to Day 1 (including unscheduled assessments).

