In an exploratory endoscopy substudy, subjects with more severe disease at the Visit 2 ileocolonoscopy (a SES-CD  $\geq$ 7, if ileum and colon are involved or  $\geq$ 4 if only the ileum is involved) will undergo a second ileocolonoscopy at the end of treatment (Day 42) to evaluate changes in the mucosa.

Pharmacokinetic (PK) evaluations will be based on concentrations of V565 measured in serum and urine. Safety will be assessed through evaluations of adverse events (AEs), clinical laboratory results, vital signs, physical examinations, electrocardiograms (ECGs) and concomitant medications.

Planned number of subjects:	Approximately 126 randomised to receive study drug in a
3	2:1 active:placebo ratio (84:42)
	Approximately 114 to complete (76:38) based on an estimated dropout
	rate of 10% during treatment

Diagnosis and main criteria for inclusion:	This study will enrol adult subjects with active CD. The main criteria for inclusion are:
	
 
History of CD (confirmed by ileocolonoscopy) of at least three months duration prior to Visit 1
 
CDAI score of ≥220 to ≤450 during Screening
 
CRP ≥5 mg/L (or, if CRP is normal, FCP ≥250 µg/g) at Screening
 
Active CD of ileum and/or colon as determined by the baseline ileocolonoscopy
 
Female subjects must not be pregnant and male and female subjects must agree to use effective contraception throughout the study and for 90 days after the last dose of study drug.
 
Subject must have failed or experienced intolerance to at least one of the following: aminosalicylates, corticosteroids; immunosuppressants (e.g., azathioprine [AZA], 6-mercaptopurine [6-MP], or methotrexate [MTX]).
 

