# 5.6 Method of Assigning Subjects to Treatment Group

Once the subject provides an informed consent and meets inclusion and exclusion criteria, the study site will request the study drug assignment using the Interactive Web Activated Response System (IWRS). Approximately 126 subjects will be randomised in a 2:1 ratio (84 subjects in the V565 arm and 42 subjects in the placebo arm). Randomisation will be stratified to ensure treatment groups have similar rates of prior anti-TNF $\alpha$  therapy.

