### 6.1.3 Biomarkers of Inflammation

The collection of CRP and/or FCP will occur at the time points indicated in .

C-reactive protein is an acute-phase reactant produced in the liver and is an easily measured non-specific marker of inflammation. It is a widely used marker of inflammation in CD and elevations in CRP have been associated with endoscopic inflammation in CD [15, 16].

C-reactive protein will be analysed in blood samples. If CRP values are normal, FCP will be assessed in the faecal samples. FCP will be used as the eligibility test if CRP results are <5 mg/L. During the treatment and follow up phase of the study, FCP will only be evaluated in subjects whose screening CRP was <5 mg/L, and who qualified for the study based on their screening FCP value.

Calprotectin is abundant in the cytosol of activated neutrophils. The amount of FCP is directly proportional to neutrophil influx into the intestinal tract and is a reliable non-specific marker of intestinal inflammation [17, 18, 19]. While currently endoscopy with biopsy is considered the gold standard for evaluating the extent and location of inflammatory mucosal lesions, studies have shown that FCP may also be a useful marker of intestinal inflammation.

On Day 1, the faecal sample for FCP should be collected prior to administration of the first dose of study drug. The subject may also provide a sample from faeces passed one day prior to the scheduled visits. These samples will be collected in sterile containers (to be provided to the subjects) and refrigerated at home. At each sampling time point, approximately 2 g to 5 g of faeces will be collected.

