# 8.2 Statistical Methods

The default summary statistics for continuous variables include number of contributing observations [n], mean, standard deviation (SD), median, minimum, and maximum.

For categorical variables, the number and percentage (the percentage of subjects in each category relative to the total number of subjects in the relevant analysis population or relative to the total number of subjects in the relevant analysis population, with assessments available [where appropriate]) in each category will be the default summary presentation.

Unless otherwise specified, "Baseline" is defined as the last observed value of the parameter of interest prior to the first intake of study medication (this includes unscheduled visits). For numerical variables, change from Baseline will be calculated as the difference between the value of interest and the corresponding baseline value.

Unless otherwise specified, all formal statistical tests will be two-sided at the 5% significance level. Point estimates of treatment differences will be accompanied with two-sided 95% confidence intervals (CIs) where applicable.

In the case of normality assumption violations, appropriate non-parametric methods will be used for analysis.

All data will be presented in by-subject listings.

The statistical analysis will be performed using SAS® Version 9.2 or higher.

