# 岌 VHsquared

STATISTICAL ANALYSIS PLAN: PROTOCOL V56502 Page 16 of 40

For the endpoints CDAI score and PRO-2, the screening score will be considered as baseline.

Listings will include scheduled and unscheduled data.

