### **6.6. S**TATISTICAL TESTS

The default significance level will be (5%); confidence intervals will be 95% and all tests will be two-sided, unless otherwise specified in the description of the analyses.

Two-sided CIs will be assessed at the 5% significance and two-sided p-value will be reported.

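### The SAP takes baseline CRP and FCP only from before Day 1, departs from the protocol's last-pre-dose rule without declaring it, and so never analyses the primary endpoint under the protocol's baseline

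*SAP*

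**What the plan says.** Protocol 8.2 gives the general rule: baseline is "defined as the last observed value of the parameter of interest prior to the first intake of study medication", subject to exceptions specified elsewhere. No exception for CRP or FCP is visible in the protocol text.

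Protocol 6.1.3 plans a pre-dose marker sample: "On Day 1, the faecal sample for FCP should be collected prior to administration of the first dose of study drug". The same section allows the sample for a visit to come from stool passed the day before. Protocol 6.2.3 has blood drawn at every visit, so a Day 1 CRP is likely, but the schedule table is not in the text available to me.

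SAP 6.2 keeps the protocol's rule as its default and treats a value on the first-dose date as pre-treatment. It then makes two exceptions. For CRP and FCP, "the baseline score is the last non-missing measurement taken prior to Day 1". The second reads: "For the endpoints CDAI score and PRO-2, the screening score will be considered as baseline".

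SAP 3.3 lists changes from the protocol. It explains why CRP and FCP leave the primary model but does not mention the marker baseline. SAP 15.1.1 chooses the marker by its baseline value: CRP if baseline CRP reaches the cut of 5, otherwise FCP. Protocol 6.1.3 measures FCP after screening only in patients who qualified on FCP.

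**The concern.** The 40% marker fall is half of the primary responder rule, and its denominator is the baseline. Three things follow from the SAP's choice.

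- The endpoint as the protocol defines it is not computed anywhere, and the reader is not told.
- If the rule is applied to collection dates, two patients attending the same Day 1 visit can have baselines from different visits. Stool passed the day before counts. Stool passed that morning does not.
- CRP of at least 5 mg/L, or FCP of at least 250 µg/g, is an entry threshold, and a re-test replaces the first result for eligibility (Protocol 4.2.1). A value selected for being high tends to be followed by a lower one without any drug effect. With no marker covariate in the model, nothing adjusts for this.

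At stake are the meaning of the reported response rates and some avoidable noise around the 40% cut.

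**Working it through.** **The plan's own figures.** Allocation is "84 subjects in the V565 arm and 42 subjects in the placebo arm". The synopsis gives "Approximately 114 to complete (76:38) based on an estimated dropout" "rate of 10% during treatment". 126 × 0.9 = 113.4, and by arm 84 × 0.9 = 75.6 and 42 × 0.9 = 37.8, which round up to 76 and 38. This reproduces. The assumed response rates and power are not visible in the text, so they cannot be checked. Tests are two-sided at 5% (SAP 6.6).

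**Assumptions, none from the documents.** Between-patient SD: 70 CDAI points (mean 280) and 0.9 log CRP (median 10 mg/L before selection). Within-patient SD: 30–60 points and 0.4–0.8 log units. Noise is independent, or correlated 0.5 from screening to Day 1 and 0.25 from Day 1 to Day 42. Mean drug effect: 60 points and 0.5 log units. Improvement common to both arms: 0, 40 or 60 points with 0, 0.3 or 0.4 log units. Patients are selected at screening on CDAI 220–450 and CRP ≥5 mg/L. The FCP route is not modelled in this grid.

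**Chance response without selection.** A 40% fall is −ln 0.6 = 0.511 on the log scale. With independent noise of SD σ and a Day 1 baseline, the chance of meeting it with no true change is Φ(−0.511/(σ√2)):

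- σ = 0.4: Φ(−0.903) = 18%
- σ = 0.6: Φ(−0.602) = 27%
- σ = 0.8: Φ(−0.452) = 33%

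**Adding selection.** With no true change, the marker criterion is met by 19–40% of patients from the screening value and by 16–33% from Day 1, correlated noise included. The excess is about 3 to 7.5 points. A separate simulation that included the FCP route gave 1.9 to 7.1 points. Most chance response is therefore ordinary variation, which any single-value baseline keeps.

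**Composite response and power.** With p̄ = (42p₀ + 84p₁)/126, SE₀ = √[p̄(1−p̄)(1/42 + 1/84)] and SE₁ = √[p₀(1−p₀)/42 + p₁(1−p₁)/84], power = Φ[(p₁ − p₀ − 1.96·SE₀)/SE₁]. For the central case (SD 45 points and 0.6 log, common improvement of 40 points and 0.3 log, independent noise):

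| Baseline | Placebo | V565 | Power |
|---|---|---|---|
| Screening, both parts | 19.7% | 48.4% | 90.4% |
| Day 1, both parts | 16.5% | 43.2% | 87.9% |
| Mean of both values, both parts | 17.3% | 47.5% | 93.6% |
| CDAI screening, marker Day 1 | 17.4% | 44.4% | 87.9% |
| CDAI screening, marker geometric mean | 18.5% | 47.7% | 91.8% |

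Across all 54 settings:

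- Day 1 for both parts lowers the placebo rate by 0.3 to 5.5 points and changes power by −7.4 to +2.1 points.
- Averaging both parts raises power by 0.2 to 5.4 points.
- I re-ran the same grid with CDAI left at screening. Day 1 for the marker alone lowers the placebo rate by 0.1 to 4.2 points and changes power by −5.8 to +1.1 points. The geometric mean of the marker alone changes power by −0.4 to +2.8 points. It is below zero in 4 of 54 settings, all with no common improvement and power above 90%.

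A separate trial-level simulation of the adjusted logistic model (30% qualifying on FCP, assumed) moved power from 89.6% to 91.0%, 79.1% to 81.6% and 68.6% to 70.4% with the marker mean: gains of 1.4, 2.5 and 1.8 points. Type I error was 4.5% with the SAP baseline and 4.0% with the marker mean.

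**What a higher placebo rate costs.** Take a fixed 25-point difference. At 20% v 45%, p̄ = 0.3667, SE₀ = 0.0911 and SE₁ = 0.0822, so power is Φ(0.870) = 80.8%. At 25% v 50%, p̄ = 0.4167, SE₀ = 0.0932 and SE₁ = 0.0863, so power is Φ(0.781) = 78.3%.

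**Marker reassignment.** In the grid, 7–18% of CRP-qualified patients have a Day 1 CRP below 5 mg/L, and 3–7% have a geometric mean below it. SAP 15.1.1 would send them to FCP, which Protocol 6.1.3 does not collect for them after screening.

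**The case against.** Protocol 8.2 allows exceptions and Protocol 8.2.6 leaves analysis detail to the SAP, so an exception in SAP 6.2 is legitimate. SAP 3.3 and the baseline list in SAP 10 suggest that the marker baseline was deliberately tied to the enrolling value. This stands as far as it goes: the SAP may choose another baseline. It should still declare and justify one that changes half of the primary endpoint, and SAP 3.3 is where it does so for other changes.

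It is also fair that the averaged baseline is in neither document, and that its gain is small and rests on assumed SDs. It is therefore a preference, while the declaration and the sensitivity run are the firm part.

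A reader might infer more than the documents support:

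- *That the choice biases the trial towards V565.* It does not. The baseline is taken before treatment and defined identically in both arms.
- *That leaving the protocol's rule costs precision.* In general it does not. The last-value rule gave equal or lower power in many settings. Precision is lost only relative to using both values.
- *That the CDAI baseline also departs from the protocol.* This is not shown. Protocol 4.1 builds the pre-treatment score from the diary and Visit 1 site data, Protocol 4.2.2 mentions only a diary compliance check on Day 1, and SAP 15.3.1.2 lists baseline, Day 14 and Day 42. If screening gives the only pre-dose score, it is the last observed one.
- *That the marker baseline is always the qualifying value and never the Day 1 visit sample.* It may be a Visit 2 or unscheduled value, or stool passed the day before Day 1.

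**Conclusion.** The point holds for CRP and FCP. SAP 6.2 replaces the protocol's last-pre-dose baseline with a value from before Day 1, sets aside a planned Day 1 FCP sample (and probably a Day 1 CRP), and does not say so in SAP 3.3. That rests on the text alone, apart from the Day 1 CRP, which the missing schedule table would confirm.

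The numerical consequences are modest. Regression to the mean adds a few points to response in both arms. The treatment comparison stays valid. Using both marker values is worth about 0 to 5 power points, where the upper end comes from averaging CDAI as well. Averaging the marker alone gives at best about 3 points and, in a few settings, a loss of less than half a point. These magnitudes depend on assumed SDs, correlations and effects and show direction and range only. The change should be made before unblinding. It does not threaten the trial's validity.

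**What to change.** 1. Set each patient's marker by the screening route that qualified them, and amend SAP 15.1.1 so that the baseline value cannot reassign it. In the same edit, reconcile the CRP unit there (mg/dL, against mg/L in the protocol) and the closing sentences of SAP 3.3, which pair entry on FCP with a fall in CRP.
2. Run the primary model with the protocol-defined last pre-dose CRP/FCP as a sensitivity analysis. List the CRP/FCP departure and its reason in SAP 3.3.
3. Preferably, define the primary marker baseline in SAP 6.2 as the geometric mean of the last screening value and the Day 1 pre-dose value of the qualifying marker, or the single value if one is missing. This also removes the dependence on when the stool was passed, provided the sample for the Day 1 visit counts as the Day 1 value whichever day it was passed.
4. CDAI may stay at screening. State whether any Day 1 CDAI exists.

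The cost is SAP wording and one extra model run, with no new FCP samples and, if Day 1 CRP is scheduled, no new blood. The downsides of item 3 are slightly lower observed response rates in most settings, a baseline that is not a single visit, and a need to confirm that bowel preparation for the Visit 2 ileocolonoscopy does not disturb the Day 1 FCP.
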